Action Plan: Recruitment: Pregnant women will be recruited from both clinical sleep referrals and obstetric clinics as in our previous studies.^{2, 4, 5, 32} Those who report snoring at least 3 nights/week will be invited to undergo a home sleep study. This approach will ensure that the majority of eligible women will be identified early in pregnancy, which will allow ample sample size to recruit from and sufficient time to initiate treatment in those enrolled and randomized to APAP. **Inclusion criteria:** < 24 weeks gestation, singleton pregnancy, and objective evidence of SDB, defined as an $AHI \geq 5$ ³³ or a respiratory disturbance index (RDI) ≥ 5 . **Exclusion criteria:** unable to give informed consent, smoking, alcohol or drug use, current PAP treatment, and multiple gestation pregnancies. Women with severe SDB ($AHI \geq 30$) or severe daytime sleepiness ($ESS > 15$) will not be randomized and instead triaged to clinical care. However, while these women will receive clinical treatment for SDB we will still follow them in an observational manner through the rest of the protocol (see below). No data exist to support or refute the hypothesis that among women with SDB, those with low AHI's may suffer less impact. Published data from small series indicate that very mild SDB during pregnancy could have profound impact on pregnancy outcomes.^{22, 34-36} Furthermore, the vast majority of pregnant women with SDB have mild-to-moderate disease. Women with $AHI \geq 5$ or $RDI \geq 5$ will be randomized to no-APAP therapy or APAP therapy using the **biased coin minimization technique**,³⁷ **a CONSORT-approved method for assignment of treatment groups in RCTs**.³⁸

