The first subject is truly random; for subsequent subjects the treatment allocation that minimizes the imbalance of selected factors between groups is identified and subjects are assigned to the treatment or non-treatment group, with higher probability being given to assignment to the group that results in the least imbalance between groups. This maintains randomness in the assignment with the advantage of making small groups closely similar for subject characteristics at all stages of the trial. Minimization is the only acceptable alternative to true randomization and may be superior.³⁹ We will use minimization to assign to the two study groups based on the following variables: blood pressure groups (hypertensive vs. not hypertensive), diabetes (diabetic vs. non-diabetic), BMI (normal vs. overweight/obese), education (high school or less vs. post-high school), and SDB severity ($AHI 5-14.9$ ($RDI 5-14.9$) vs. $AHI 15-29.9$ ($RDI 15$ and above)). Women with an $AHI \geq 30$ or a daytime sleepiness score ≥ 16 on the Epworth Sleepiness Scale⁴⁰ will not be randomized and will be referred for clinical APAP care. However, these women will still undergo the 3rd trimester assessments (see below).

Polysomnography and APAP: Ambulatory polysomnography will be used to determine SDB status at baseline. We have previously validated home-based polysomnography in pregnant women.³² Following the nocturnal study, data will be down-loaded and analyzed using criteria of the American Academy of Sleep Medicine.³³ Women with SDB will be randomized to APAP therapy; use of auto-titrating machines allows delivery of the lowest effective pressure without need for multiple in-laboratory re-titrations as pregnancy progresses. Women will use APAP for the remainder of their pregnancies and will be closely followed by the study team. This will include remote monitoring of adherence, a major strength of our prior work. Ambulatory polysomnography will be repeated at 32-weeks with the addition of nocturnal fetal monitoring. Any woman in the non-APAP group who

no longer has SDB in the 3rd trimester will not be included in the final analysis. In our experience it is uncommon, although not impossible, for a women with SDB early in pregnancy to no longer have SDB in the 3rd trimester. Typically the severity of SDB worsens as pregnancy progresses. Nonetheless, to ensure that all non-APAP women still have SDB in the 3rd trimester it is important to repeat the sleep study in the 3rd trimester.

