Potential Problems and Alternative Strategies: Although our preliminary data solidly support the hypotheses there is the possibility that no differences will be found for fetal growth trajectory. In the unlikely even that this occurs, we will examine fetal heart rate variables and subjective measures of fetal movement for any subtle signs of fetal compromise that may not translate to large enough insults to significantly affect fetal growth measures but which may aid in the understanding of fetal wellbeing. Another potential problem is that insufficient women with SDB will be identified. However, given the large pool of women (approximately 4500/year) we do not foresee problems with recruitment. Although infrequent, it is possible that women with SDB in early pregnancy may not meet the threshold later in pregnancy. To minimize this (as well as drop out for other reasons), we will over-enroll women to allow our final sample size to be sufficient for analysis (at least 27 women per group). Women could decline to undergo home monitoring; this is not likely to occur, since >50% of high and low-risk women approached for home monitoring have enrolled in our protocols. An additional potential problem is the use and adherence to APAP. However, we have previously demonstrated our ability to maintain adherence in 80% of pregnant women in a longitudinal study of APAP therapy in hypertensive pregnancies, of which about half did not even meet present criteria for SDB (K23HL095739); of those with SDB, we were able to maintain adherence in >90%. Our success was due to the ability to build a strong rapport along with frequent contact. The current study will only randomize women with SDB and thus, we believe that we are in a strong position to retain sufficient women on APAP. A further possibility exists in that no differences in gross placental pathology will be found. However, histological differences may still be present. If markers of hypoxia are not found, we will use the banked placental tissue to investigate the presence of angiogenic factors and receptors e.g., vascular endothelial growth factor, placental growth factor, and soluble fms-like tyrosine kinase 1. We will also investigate neutrophil extracellular traps as we have previously described⁴⁵ or epigenetic changes.

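### AHI of 30 or more triggers referral for APAP at entry, but the protocol text supplied attaches no action to the same result in a no-APAP control at 32 weeks

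*Combined protocol and SAP*

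**What the plan says.** **Entry rule.** The Action Plan states the severity limit twice. Under Recruitment, women with AHI of 30 or more, or an Epworth score above 15, "will not be randomized and instead triaged to clinical care". The paragraph on minimisation repeats that they "will not be randomized and will be referred for clinical APAP care". They stay in observational follow-up. The upper severity stratum for randomised women is AHI 15 to 29.9, so a control may start just below the limit.

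**Expected course.** Polysomnography and APAP says: "Typically the severity of SDB worsens as pregnancy progresses". Recruitment also says that "the vast majority of pregnant women with SDB have mild-to-moderate disease".

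**The repeat test.** "Ambulatory polysomnography will be repeated at 32-weeks with the addition of nocturnal fetal monitoring". Besides serving as the occasion for fetal monitoring, the repeat is needed "to ensure that all non-APAP women still have SDB in the 3rd trimester". One consequence is stated: a non-APAP woman who "no longer has SDB in the 3rd trimester will not be included in the final analysis".

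**Contingencies.** Potential Problems and Alternative Strategies considers the downward direction only: "it is possible that women with SDB in early pregnancy may not meet the threshold later in pregnancy".

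**The concern.** The plan sets its own limit above which a woman should go to clinical treatment rather than risk allocation to no APAP. It applies that limit once, before 24 weeks. At least eight weeks later it measures the same quantity again, in women it expects on the whole to have worsened, and gives a rule only for those who improved.

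The main stake is participant safety. The study team could hold a result above the plan's own referral limit, and the text supplied would place no duty on them to act on it.

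A lesser stake is interpretation. If such a woman does start APAP, nothing says how she is analysed. Several outcomes come after the 32-week test: the 36-week scan, the 36-week fetal movement assessment, birth weight, gestational age at birth and the placenta.

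**Working it through.** **1. Search for a rule.** The parts of the document that could hold one are set side by side.

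| Place | What it says about a severe result after randomisation |
|---|---|
| Recruitment; minimisation paragraph | Entry only: refer, do not randomise, follow up |
| Polysomnography and APAP | Drop controls whose SDB has resolved; nothing on severe results |
| Potential Problems and Alternative Strategies | Falling below the SDB threshold only |
| Evaluation and Analytic approach | No rescue or crossover rule |
| Covid19 amendment March 2020 | How the test is delivered, not what follows from it |
| Amendments | Retains women triaged as severe; adds a sleep physician; no 32-week action |

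No referral, notification, rescue or crossover rule tied to the 32-week result appears.

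**2. How often it might arise.** The documents give no rate at which controls pass AHI 30. The rates below are therefore pure assumption. With a crossing rate r, the chance of at least one such woman among 30 controls is 1 − (1 − r)^30.

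| Assumed r | Expected number (30r) | Chance of at least one |
|---|---|---|
| 0.1% | 0.03 | 3% |
| 0.5% | 0.15 | 14% |
| 1% | 0.3 | 26% |
| 2% | 0.6 | 45% |
| 5% | 1.5 | 79% |
| 10% | 3.0 | 96% |

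The range runs from unlikely to nearly certain. The table shows only that the event cannot be dismissed; it is not an estimate.

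**3. What referral would cost in power.** Birth weight is used because it is the only outcome the plan powers; the main outcome is growth trajectory.

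- Inputs from Sample Size and Power Calculation: means 2485 g and 3036 g, SD 625 g, alpha 0.05, 30 enrolled per group. Potential Problems gives at least 27 per group for analysis. A two-sided test is assumed, since the plan does not state sidedness.
- Difference: 3036 − 2485 = 551 g.
- Plan's own figure: the normal approximation gives 90.0% power at 27 per group, as stated. The t-test gives 88.9% at 27 and 91.9% at 30.
- Worst case: each of k controls who start APAP after 32 weeks gains the whole 551 g. The difference becomes 551 × (1 − k/n).

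| n per group | k | Difference | t-test power |
|---|---|---|---|
| 30 | 0 | 551 g | 91.9% |
| 30 | 2 | 551 × 28/30 = 514 g | 88.0% |
| 27 | 0 | 551 g | 88.9% |
| 27 | 2 | 551 × 25/27 = 510 g | 83.7% |

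A simulation at 30 per group that shifts two individual controls by 551 g gives 87.4%, close to the formula. The real loss should be smaller, because APAP would cover only the weeks from the test to delivery.

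**The case against.** The strongest reply is that silence is not a prohibition. No text bars clinical care for a control. A clinical triage route exists, some women come from sleep referrals, and a sleep physician is on the team. The consent pages, a natural place for a rule on acting on results, were removed from the copy reviewed. A reader might infer that a control at AHI 30 or more is kept off APAP for the rest of her pregnancy. The documents do not support that: they neither require nor prevent referral. This part of the objection stands, and the point is limited to the absence of a requirement in the text supplied.

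A reader might also infer that controls are expected to reach AHI 30. That is not supported either. The plan expects worsening in general and describes most SDB in pregnancy as mild to moderate.

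It can further be said that the cost of referral is larger than it looks at 30 per group. That is correct at the plan's minimum of 27, and both figures are given. In the other direction, research ultrasounds for women not on active APAP were cancelled during the Covid period, so some controls may have no 36-week scan to dilute.

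What the objection does not remove is the asymmetry. The plan wrote down its severity rule for entry rather than leaving it to discretion, and it wrote down a rule for the 32-week result in the direction it calls infrequent. The direction it calls typical has none.

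**Conclusion.** The gap is real within the protocol text supplied, and the plan should close it. The plan's own limit for referral has no counterpart at the 32-week test, although that test measures the same index. Confidence is high that the text contains no such rule. It is much lower on the practical consequence, which depends on what clinicians would do anyway and on documents not seen. The number of women affected cannot be estimated from the documents. The interpretability issue is minor. The power figures are worst-case illustrations that assume two women cross and each gains the full 551 g.

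**What to change.** Add to Polysomnography and APAP wording such as:

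> Any woman in the non-APAP group with AHI of 30 or more at the 32-week sleep study (or an Epworth score of 16 or more, if the scale is repeated) is promptly reviewed by the study sleep physician and referred for clinical APAP care, as at entry. She stays in follow-up and is analysed in her randomised arm. The APAP start date and the number of such women are reported.

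The Epworth clause is conditional because the documents do not say that the scale is repeated. If an equivalent rule already stands in the consent form or a safety plan, a cross-reference plus the analysis sentence is enough.

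The operational cost is one amendment and prompt reading of a test already scheduled; the referral route with continued follow-up already exists. The statistical cost is modest dilution of outcomes after 32 weeks, at most about 4 to 5 percentage points of birth-weight power in the two-woman worst case.

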Maternal sleep disruption, specifically SDB, has emerged as a predictor of poor maternal outcomes. Symptoms of SDB affect up to 15% of women at conception,^{2, 14} up to 35% of women in the 3rd trimester,^{1 2} and up to 85% of women with hypertensive disorders of pregnancy.^{4, 15} Objectively-diagnosed SDB has been found in 8% of all pregnant women by mid-gestation,¹⁶ 15% of obese pregnant women,¹⁴ and approximately half of hypertensive pregnancy women.^{4, 15} There is now a wealth of literature that demonstrates independent associations between maternal SDB and gestational hypertension, preeclampsia, and gestational diabetes.^{2, 17- 20} Maternal SDB has also been associated with FGR,^{6, 19} including a large study by our group.⁷ In some exciting and novel preliminary data we have demonstrated that APAP use in pregnancy is associated with improved infant birth weight: infants born to women who used APAP during pregnancy (n=18), compared to infants born to women with SDB who did not use APAP (n=17), have larger birth weight (3036±833g vs. 2485±1050g, p=0.08) even after accounting for duration of PAP use. In addition, we have preliminary data to show that APAP in pregnancy is associated with longer gestation; women who used APAP (n=18) continued their pregnancies for a mean of 2.5±3.4 weeks longer than those who did not use PAP (n=17; 37.7±2.8 weeks vs. 35.1±4.1 weeks, p=0.03). *This is a clinically significant duration that will have long-term impact on infant health.* Moreover, in a retrospective study we have data to show that fetuses of women with SDB have a fall in growth across the centiles, a pattern that was not present in women using APAP therapy.²¹ In a small pilot study it has recently been reported that SDB in women with preeclampsia is associated with reduced fetal movement, which was partially reversed with APAP therapy.²² Taken together, these preliminary findings suggest that APAP treatment of pregnant women with SDB is a window of opportunity to provide an urgently-needed clinical intervention that will improve fetal growth trajectory and thus have a positive impact on not only short-term pregnancy outcomes but also on longer-term morbidity.

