
Fetal Assessment: Fetal growth: Women will undergo traditional Doppler ultrasounds three times during the 3rd trimester (28, 32, and 36 weeks) for estimated fetal weight which will be adjusted for key, non-pathological maternal variables known to affect fetal growth, using the US dataset of the GROW software.⁴¹ Such customization is superior to population-based fetal weight standards as it generates an in utero growth standard that is customized for each fetus, to adjust for relevant maternal characteristics that may impact fetal growth. Thus the growth is optimized to obtain the growth potential of the fetus in the absence of pathology such as smoking, preeclampsia, or diabetes. Birth weight and gestational age will be abstracted from medical records. Birth weight will be converted into an adjusted birth centile using the GROW software.⁴¹ The purpose is to calculate the 'term optimal weight' as an ideal standard, against which the actual weight can be assessed. We have successfully used this software in a previous large cohort study.⁵ During a second home sleep study in the 3rd trimester women will undergo in-home continuous portable fetal monitoring using the Monica DK, a small Holter-type device (Nottingham, UK), which has been validated against cardiotocography.⁴²⁻⁴⁴ Patterns of fetal movement will be assessed at the same three time-points in the third trimester as the ultrasounds.

Placental Pathology: At the time of delivery, 3 full-thickness placental disc samples will be obtained and processed in routine fashion. Gross placental pathology will be performed including placental weight, and fetoplacental weight ratio. Histologic examination will be conducted using a rigorous, methodical pathologic review adapted from Salafia & Popek³¹ and developed with the intention of identifying underlying pathophysiologic processes. These factors include acute and chronic inflammation, uteroplacental vascular pathology and villous lesions, and intraplacental vascular pathology. This examination was piloted⁴⁵ and refined in our preliminary analysis of placental tissue. Samples of placental tissue will also be banked for future research.

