Sample Size and Power Calculation: To estimate the sample size required to detect a clinically important difference between groups we calculated the difference in birth weight between newborns of women with SDB who used APAP vs. those who did not use APAP, using a linear regression model which accounted for length of APAP use. From preliminary data of n=18 APAP users and n=17 non-PAP users, the APAP users delivered infants who were 551grams (over 1 pound) larger than non-APAP users. Assuming a mean birth weight of 2485g for the SDB group and 3036g for the APAP group with a standard deviation of 625g, a sample size of n=27 per group has 90% power to detect a difference with $\alpha=0.05$. Even with a sample size of n=21 per group, we would

still have >80% power to detect this difference. We are therefore confident that our milestones will be obtained if we enroll n=30 women per group. There is ample power to detect a clinically significant endpoint.

Statement of how patients will be recruited and retained:

Recruitment: Pregnant women will be recruited from obstetric clinics as described above. Our wealth of experience in conducting sleep-related protocols with pregnant women has allowed efficient, targeted screening in order to identify those at highest risk of SDB, and reserving objective confirmatory testing to those likely to provide the highest yield of SDB diagnoses. Our preliminary data demonstrate that report of habitual snoring (snoring ≥ 3 nights per week) is an excellent marker for the presence of objectively confirmed SDB. In a group of n=67 pregnant women (mean gestational age 28.2 ± 7.8 weeks) who underwent polysomnography, mean AHI was significantly higher in habitually snoring pregnant women compared to non-snoring pregnant women (17.3 vs. 3.3; $p < 0.01$). We found that habitual snoring has good sensitivity (0.80), specificity (0.77), positive (0.70) and negative (0.90) predictive value for identifying women with confirmed SDB. Our approach thus minimizes the need for widespread objective testing. Furthermore, we have successfully treated pregnant women with APAP. Of n=51 pregnant women with SDB who were offered PAP (K23 HL095739) we enrolled n=45 women (88% of invited).

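### The 551 g planning difference is the pilot's birth-weight gap unadjusted for a 2.6-week difference in delivery, so the stated 90% power applies to raw birth weight and not to growth at a given gestation

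*Combined protocol and SAP*

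**What the plan says.** Under Sample Size and Power Calculation, the planning effect is a birth-weight difference between pilot women with SDB who did and did not use APAP, obtained "using a linear regression model which accounted for length of APAP use". The result given is that "the APAP users delivered infants who were 551grams (over 1 pound) larger than non-APAP users". The calculation then proceeds "Assuming a mean birth weight of 2485g for the SDB group and 3036g for the APAP group", and "with a standard deviation of 625g, a sample size of n=27 per group has 90% power". A fallback of 21 per group is said to keep power above 80%, and the paragraph closes: "There is ample power to detect a clinically significant endpoint".

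The Background section gives the pilot data: birth weight 3036±833 g in 18 APAP users and 2485±1050 g in 17 non-users (p=0.08). It also gives gestation at delivery for groups of the same labels and sizes: "37.7±2.8 weeks vs. 35.1±4.1 weeks, p=0.03". The gestation difference is printed there as 2.5 weeks; the two means differ by 2.6.

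The main outcome, named under EVALUATION, is longitudinal fetal growth trajectory. Under Fetal Assessment, estimated fetal weight is measured by ultrasound at 28, 32 and 36 weeks and adjusted with the GROW software. Birth weight is not to be used raw either: "Birth weight will be converted into an adjusted birth centile using the GROW software". The plan gives no power calculation for trajectory or centile.

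**The concern.** A fetus that stays in the uterus longer weighs more at birth even if its growth curve is unchanged. The pilot groups delivered more than two weeks apart, so some of the 551 g could arise with no difference in growth. A scan at a fixed gestation, or a centile that compares weight with a standard for the same gestation, does not credit that component.

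The covariate named in the pilot regression does not deal with this. Length of APAP use is zero for every non-user, so it cannot remove a between-group difference in gestation. Among users it tends to be shorter when delivery is earlier.

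What is at stake is how the result is read. The only power statement in the plan is for a quantity that includes prolongation of pregnancy. If the growth comparison is null, a reader who takes the 90% at face value would regard it as a well-powered negative test of growth.

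**Working it through.** **1. Reproduce the plan's figure.** Inputs from the sample size section: difference 551 g, SD 625 g, 27 per group, α = 0.05 (taken as two-sided, which is the variant that matches). Standard error = 625 × √(2/27) = 170.1 g; 551/170.1 = 3.24; power = Φ(3.24 − 1.96) = 0.900. The t-based value is 0.889. At 21 per group, power is 0.815 (normal) or 0.796 (t). The arithmetic is sound.

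**2. Identify the 551 g.** 3036 − 2485 = 551, the difference between the means printed as mean±SD in Background. An equal-variance t-test on those summaries gives p = 0.094, not the printed 0.08. The printed p may therefore come from another model, but that does not settle which estimate the 551 g is.

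**3. Break-even weekly gain.** The documents give no weight gain per week. With the gap from the means, 37.7 − 35.1 = 2.6 weeks, all of the 551 g is explained at 551/2.6 = 212 g/week and half at 106 g/week. With the printed 2.5 weeks the values are 220 and 110 g/week.

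**4. Range from the pilot's own spread.** Pooled SD of birth weight = √[(17×833² + 16×1050²)/33] = 944 g. Pooled SD of gestation = √[(17×2.8² + 16×4.1²)/33] = 3.49 weeks. For an assumed within-group correlation r (not in the documents), slope = r × 944/3.49, explained = 2.6 × slope, remainder = 551 − explained, residual SD = 944 × √(1 − r²). Power is by two-sided t-test at 27 per group.

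| r | slope, g/week | explained, g (%) | remainder, g | power, SD 625 | power, residual SD |
|---|---|---|---|---|---|
| 0.4 | 108 | 281 (51%) | 270 | 34% | 20% |
| 0.5 | 135 | 352 (64%) | 199 | 21% | 14% |
| 0.6 | 162 | 422 (77%) | 129 | 12% | 9% |
| 0.7 | 189 | 492 (89%) | 59 | 6% | 6% |
| 0.8 | 216 | 563 (102%) | −12 | 5% | 5% |
| 0.9 | 243 | 633 (115%) | −82 | 8% | 11% |

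In the last two rows the remainder favours no APAP, so the power shown is not power to find a benefit.

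**5. Sensitivity to the SD in the slope.** Using 625 g in place of 944 g, the slope is r × 625/3.49. At r = 0.6 this explains 279 g (51%) and leaves 272 g, with power 35% (SD 625) or 50% (residual SD 500). At r = 0.9 it explains 419 g (76%) and leaves 132 g, with power 12% or 42% (residual SD 272). Over r = 0.6 to 0.9 the range is 12–50%.

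**6. Sensitivity to the weekly gain directly.** At an assumed 100 g/week, 551 − 260 = 291 g remains: power 39% at SD 625, 75% at an assumed SD of 400 g. At 150 g/week, 161 g remains: 15% and 31%. Power above 90% returns only with a slow gain and a much smaller SD together: 50 g/week leaves 421 g, with power 97% at SD 400 but 68% at SD 625.

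**The case against.** The strongest reply is that gestation is not a nuisance here. Background presents longer pregnancy as associated with APAP and clinically important, and links growth restriction with preterm birth. Gestation at delivery may therefore lie on the causal path. In a randomised comparison, raw birth weight including any prolongation is a legitimate total effect, and the 90% could be a fair statement about it. This stands. It limits the point to what the power figure describes, and it means that adjusting for gestation at delivery carries its own caveat as a post-randomisation variable. It does not make raw birth weight the main outcome.

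A second reply is that the size of the problem rests on figures the plan does not contain. That also stands. A reader might infer that most or all of the 551 g is gestation, or that the trial's power for growth is around 5–12%. Those statements need r of 0.6 or more together with the 944 g slope SD. With r = 0.4, or with 625 g in the slope, the explained share falls to about half and the power rises.

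Third, the calculation is not wrong as arithmetic, and someone who has not seen the pilot regression cannot say its description is false. Both are accepted. The exact match to the raw gap justifies a request to clarify, not deletion of the description.

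Finally, the amendment log shows women already in follow-up by spring 2020, so the correction bears on interpretation more than on design.

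**Conclusion.** The point holds in a limited form. The 551 g equals the unadjusted gap between the pilot means, no adjustment for gestation is described, and groups of the same labels and sizes delivered 2.6 weeks apart. Background does not expressly say that the two comparisons used the same women. The 90% and >80% figures therefore apply to raw birth weight including any effect on gestation, and the plan has no power statement for growth at a given gestation.

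The share due to gestation is not determinable from the documents. With r from 0.4 to 0.9 and the pilot SDs, it is about 51–115%, and power for the remainder is about 5–34%. With a 625 g slope SD and r from 0.6 to 0.9, it is 51–76% and about 12–50%. All of these are well under 90%, but they describe gestation-adjusted birth weight, which is only a proxy. A reader might take them as the power of the multi-level trajectory analysis. The documents do not support that, because they give no variance or effect size for the trajectory. Nor do they support the inference that the sample size must change. Separately, the pilot SDs pool to 944 g rather than 625 g; the source of 625 g deserves its own explanation and is not needed for this conclusion.

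**What to change.** All changes fall in the sample size paragraph; no change in sample size is proposed.

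1. Label 551 g as unadjusted for gestation at delivery, and state that the 90% and >80% figures refer to raw birth weight including any effect of APAP on length of gestation.
2. From the same 35 pilot women, recompute the difference as a gestation-specific GROW centile or z-score (or as gestation-adjusted birth weight), with the residual SD on that same scale. Restate power at 27 per group from that pair; the 625 g SD should not be carried over. Say that this is still a birth measure and only a proxy for the ultrasound trajectory, and that gestation at delivery may itself be affected by APAP.
3. State whether 551 g is the raw difference or the regression estimate, and correct the description to match.
4. Remove or qualify the closing sentence, "There is ample power to detect a clinically significant endpoint".

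The cost is a short re-analysis of pilot data already held, the rewording of one paragraph, and a stated power for growth that is likely to be less favourable than 90%.
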